### **5.1.1 Risks Associated with Atezolizumab**

Atezolizumab has been associated with risks such as the following: IRRs and immune-mediated hepatitis, pneumonitis, colitis, pancreatitis, diabetes mellitus, hypothyroidism, hyperthyroidism, adrenal insufficiency, hypophysitis, Guillain-Barré syndrome, myasthenic syndrome or myasthenia gravis, meningoencephalitis, myocarditis, nephritis, myositis, and severe cutaneous adverse reactions. Immune-mediated reactions may involve any organ system and may lead to hemophagocytic lymphohistiocytosis (HLH) and macrophage activation syndrome (MAS), which are considered to be potential risks for atezolizumab.

Refer to [Appendix 11](#) and Section 6 of the latest version of the Atezolizumab Investigator's Brochure for a detailed description of anticipated safety risks for atezolizumab, including the occurrence of serious, related and unexpected events.

*Guidelines for managing patients who experience anticipated adverse events are provided in [Appendix 11](#).*

### **5.1.2 Management of Patients Who Experience Specific Adverse Events**

#### ***Dose Modifications***

There will be no dose modifications for atezolizumab in this study.

#### ***Treatment Interruption***

Atezolizumab may be temporarily suspended in patients who experience toxicity considered to be related to study treatment. If atezolizumab is withheld for > 12 weeks, the patient will be discontinued from study drug. *Atezolizumab can be resumed after being withheld for >12 weeks if the patient is likely to derive clinical benefit. The decision to re-challenge patients with atezolizumab should be based on investigator's assessment of benefit-risk and documented by the investigator. The Medical Monitor is available to advise as needed. Atezolizumab treatment may be suspended for reasons other than toxicity (e.g., surgical procedures).* If a patient must be tapered off steroids

that have been used to treat adverse events, then atezolizumab may be withheld for more than 12 weeks from the last dose until the steroids are discontinued or reduced to a prednisone dose (or dose equivalent) of  $\leq 10$  mg/day. For patients with CNS metastases or autoimmune disease who require chronic steroid therapy, who have been receiving additional steroids to treat adverse events, and who now require a reduction in steroid dosage, atezolizumab may be withheld for more than 12 weeks from the last dose until the steroid dosage has returned to its baseline value. The investigator will determine the acceptable length of treatment interruption. The acceptable length of treatment interruption *must be based on an assessment of benefit–risk by the investigator and in alignment with the protocol requirements for the duration of treatment and documented by the investigator. The Medical Monitor is available to advise as needed.*

For the management of atezolizumab related adverse events please refer to [Appendix 11](#) and Section 6 of the latest version of the Investigator's Brochure.

For patients developing a new autoimmune disease not listed in [Appendix 11](#) and Section 6 of the latest version of the Atezolizumab Investigator's Brochure, or for patients with an autoimmune disease who develop a flare, the following dosing guidance should be applied:

- Grade 1 event: atezolizumab dosage should be maintained
- Grade 2 or 3 event: atezolizumab should be suspended until the subject responds to treatment of the autoimmune disease and the disease becomes stable (see rules above regarding maximum suspended time). The subject should be referred to an appropriate specialist
- Grade 4 event: atezolizumab should be permanently discontinued and the subject should be referred to an appropriate specialist

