9. Life expectancy  $\geq$  12 weeks
10. Adequate hematologic and end-organ function, defined by the following laboratory results obtained within 2 weeks prior to the first study treatment:
  - Absolute neutrophil count  $\geq$  1500 cells/ $\mu$ L (without granulocyte colony-stimulating factor support within 2 weeks prior to the first study treatment)
  - White blood cell count  $>$  2500/ $\mu$ L
  - Lymphocyte count  $\geq$  500/ $\mu$ L
  - Platelet count  $\geq$  100,000/ $\mu$ L (without transfusion within 2 weeks prior to the first study treatment)
  - Hemoglobin  $\geq$  9.0 g/dL (patients may be transfused or receive erythropoietic treatment to meet this criterion)
  - Aspartate transaminase (AST), alanine transaminase (ALT), and alkaline phosphatase  $\leq$  2.5 times the upper limit of normal (ULN), with the following exceptions:
    - Patients with documented liver metastases: AST and/or ALT  $\leq$  5  $\times$  ULN
    - Patients with documented liver or bone metastases: alkaline phosphatase  $\leq$  5  $\times$  ULN
  - Serum bilirubin  $\leq$  1.5  $\times$  ULN. Patients with known Gilbert disease who have serum bilirubin level  $\leq$  3  $\times$  ULN may be enrolled
  - Calculated creatinine clearance  $\geq$  15 mL/min (Cockcroft-Gault formula)
  - International normalized ratio (INR) and activated partial thromboplastin time (aPTT)  $\leq$  1.5  $\times$  ULN. This applies only to patients who are not receiving therapeutic anticoagulation; patients receiving therapeutic anticoagulation must be on a stable dose
11. Patients with treated, asymptomatic central nervous system (CNS) metastases are eligible, provided they meet all of the following criteria:
  - Evaluable disease outside the CNS

- No history of intracranial or spinal cord hemorrhage
- No evidence of significant vasogenic edema
- No stereotactic radiation within 7 days or whole-brain radiation or neurosurgical resection within 2 weeks before the start of study treatment
- Have had a screening CNS radiography  $\geq$  2 weeks since completion of radiotherapy or surgical resection
- Radiographic demonstration of interim stability (i.e. no progression) between the completion of CNS-directed therapy and the screening radiographic study

Note: Patients on stable doses of anticonvulsants or on prednisone doses (or dose equivalents) of  $\leq$  20 mg/day are allowed

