22. Specifically for patients without autoimmune disease: treatment with systemic corticosteroids or other systemic immunosuppressive medications (including, but not limited to, prednisone, dexamethasone, cyclophosphamide, azathioprine, methotrexate, thalidomide, and anti-tumor necrosis factor agents) within 2 weeks prior to study treatment initiation or anticipated requirement for systemic immunosuppressive medications during the study treatment period
  - For patients with CNS metastases, use of prednisone at a dose (or dose equivalent) of  $\leq$  20 mg/day is acceptable
  - Chronic use of prednisone or equivalent should be discussed with the Medical Monitor
  - The use of inhaled corticosteroids for chronic obstructive pulmonary disease, mineralocorticoids (e.g., fludrocortisone) for patients with orthostatic hypotension, and low-dose supplemental corticosteroids for adrenocortical insufficiency and topical steroids for cutaneous diseases are allowed.

Note: For patients with autoimmune disease, immunosuppressive medications are permitted if the patient has controlled autoimmune disease and stable treatment (i.e., same treatment, same dose) for the previous 12 weeks.

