#### **TREATMENT INTERRUPTION**

Atezolizumab treatment may be temporarily suspended in patients experiencing toxicity considered to be related to study treatment. If corticosteroids are initiated for treatment of the toxicity, they must be tapered over  $\geq 1$  month to  $\leq 10$  mg/day oral prednisone or equivalent before atezolizumab can be resumed. If atezolizumab is withheld for  $> 12$  weeks after event onset, the patient will be discontinued from atezolizumab. However, atezolizumab may be withheld for  $> 12$  weeks to allow for patients to taper off corticosteroids prior to resuming treatment. Atezolizumab can be resumed after being withheld for  $> 12$  weeks if the patient is likely to derive clinical benefit. *The decision to re-challenge patients with atezolizumab should be based on investigator's assessment of benefit–risk and documented by the investigator. The Medical Monitor is available to advise as needed. Atezolizumab treatment may be suspended for reasons other than toxicity (e.g., surgical procedures). The acceptable length of treatment interruption must be based on an assessment of benefit–risk by the investigator and in alignment with the protocol requirements for the duration of treatment and documented by the investigator. The Medical Monitor is available to advise as needed.*

**Appendix 11: Risks Associated with Atezolizumab and Guidelines for Management of Adverse Events Associated with Atezolizumab (cont.)**

---

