**Table 1 Management Guidelines for Pulmonary Events, Including Pneumonitis**

Event	Management
Pulmonary event, Grade 1	
 
Continue atezolizumab and monitor closely.
 
Re-evaluate on serial imaging.
 
Consider patient referral to pulmonary specialist.
 
For Grade 1 pneumonitis, consider withholding atezolizumab.
 

Pulmonary event, Grade 2	
 
Withhold atezolizumab for up to 12 weeks after event onset.a
 
Refer patient to pulmonary and infectious disease specialists and consider bronchoscopy or BAL.
 
Initiate treatment with 1–2 mg/kg/day oral prednisone or equivalent.
 
If event resolves to Grade 1 or better, resume atezolizumab.b
 
If event does not resolve to Grade 1 or better while withholding atezolizumab, permanently discontinue atezolizumab and contact Medical Monitor.c
 
For recurrent events or events with no improvement after 48–72 hours of corticosteroids, treat as a Grade 3 or 4 event.
 

Pulmonary event, Grade 3 or 4	
 
Permanently discontinue atezolizumab and contact Medical Monitor.c
 
Bronchoscopy or BAL is recommended.
 
Initiate treatment with 1–2 mg/kg/day IV methylprednisolone or equivalent.
 
If event does not improve within 48 hours after initiating corticosteroids, consider adding an immunosuppressive agent.
 
If event resolves to Grade 1 or better, taper corticosteroids over <math>\geq 1</math> month.
 

BAL = bronchoscopic alveolar lavage.

a Atezolizumab may be withheld for a longer period of time (i.e.,  $> 12$  weeks after event onset) to allow for corticosteroids (if initiated) to be reduced to the equivalent of  $\leq 10$  mg/day oral prednisone. The acceptable length of the extended period of time must be based on an assessment of benefit–risk by the investigator and in alignment with the protocol requirements for the duration of treatment and documented by the investigator. The Medical Monitor is available to advise as needed.

b If corticosteroids have been initiated, they must be tapered over  $\geq 1$  month to the equivalent of  $\leq 10$  mg/day oral prednisone before atezolizumab can be resumed.

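### The chronic-steroid end point for withholding atezolizumab in Section 5.1.2 (return to the baseline dose) is missing from Appendix 11, which ties resumption to 10 mg/day prednisone or less; for eligible patients with a baseline above 10 mg/day the two texts need to be reconciled

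*Protocol*

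**What the plan says.** **Protocol Section 5.1.2, Treatment Interruption.** Two sentences deal with steroids given for adverse events.

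- In general, atezolizumab may be withheld for more than 12 weeks "until the steroids are discontinued or reduced to a prednisone dose (or dose equivalent) of" 10 mg/day or less.
- A second sentence covers a narrower group, whose dose must then come down again: "For patients with CNS metastases or autoimmune disease who require chronic steroid therapy, who have been receiving additional steroids to treat adverse events". In this group the hold may run "from the last dose until the steroid dosage has returned to its baseline value". It gives no mg/day figure and no minimum taper.

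The section then sends the reader to Appendix 11 for managing related adverse events. It does not say which text governs if they differ.

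**Protocol Appendix 11, Treatment Interruption.** "If corticosteroids are initiated for treatment of the toxicity, they must be tapered over" at least 1 month, to no more than 10 "mg/day oral prednisone or equivalent before atezolizumab can be resumed". Footnote b repeats this ("If corticosteroids have been initiated, they must be tapered over" at least 1 month) under Tables 1–5, 8–10, 12 and 13. Footnote a in the same tables allows a hold beyond 12 weeks so that steroids can come down to 10 mg/day or less. None of these places mentions return to a baseline dose.

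**Eligibility.** Section 4.1.1, criterion 11: "Patients on stable doses of anticonvulsants or on prednisone doses (or dose equivalents) of" 20 mg/day or less are allowed in treated CNS disease. Section 4.4.2 repeats that ceiling for use on study. Section 4.1.2, criterion 22, on autoimmune disease: "immunosuppressive medications are permitted if the patient has controlled autoimmune disease and stable treatment" for the previous 12 weeks, with no dose ceiling.

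**The concern.** The trial deliberately broadened entry to patients with CNS metastases on low-dose steroids and to patients with controlled autoimmune disease (Section 1.4). The same section names the drug-interruption criteria of Section 5.1.2 as a safety measure. These are the patients for whom the section writes a special sentence, yet the appendix it points to for day-to-day management omits it.

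Two things are at stake. First, a site treating such a patient after an immune-mediated event may find the steroid condition for resuming met in one place and not in the other. Second, CNS metastases, autoimmune disease and steroid treatment ongoing at baseline are pre-specified subgroups (Protocol Section 6.6; SAP Sections 4.4.5 and 4.6.2). Exposure and discontinuation are also reported (SAP Sections 4.2 and 4.6.1). Which text a site follows could affect who restarts within those subgroups.

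**Working it through.** The plan has no figure to reproduce here, so the check compares the texts across the baseline doses that eligibility allows.

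**Step 1: compare sentences with the same function.** The chronic-user sentence of Section 5.1.2 and footnote a of Appendix 11 both extend a hold beyond 12 weeks to let steroids come down. Their end points differ: the patient's own baseline dose in one, 10 mg/day or less in the other. Appendix 11 then makes the second end point, with the taper, a condition for resuming.

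**Step 2: total or added dose?** Appendix 11 does not say. Section 5.1.2 gives the 10 mg/day end point and then a separate end point for chronic users. The most natural reason is that 10 mg/day is a total dose, which someone with a higher baseline could not reach by stopping the extra steroid alone. This is an inference from structure, not a stated definition.

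**Step 3: apply both texts, with 10 mg/day read as a total dose.**

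| Baseline prednisone equivalent | Section 5.1.2 end point | Appendix 11 limit | Result |
|---|---|---|---|
| 10 mg/day or less | baseline | 10 mg/day | Baseline dose satisfies both; only Appendix 11 states a minimum taper |
| Above 10, up to 20 mg/day (CNS metastases) | baseline, at most 20 mg/day | 10 mg/day | Excess of up to 20 − 10 = 10 mg/day; ratio up to 20 / 10 = 2 |
| Above 10 mg/day (autoimmune disease) | baseline, no ceiling | 10 mg/day | Excess has no stated upper bound |

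In the last two rows a patient back at baseline has reached the Section 5.1.2 end point but cannot meet Appendix 11 without going below the chronic dose.

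**Step 4: apply both texts, with 10 mg/day read as added steroid only.** Appendix 11 then limits what remains of the extra steroid. Section 5.1.2 permits, but does not compel, holding until all of it is gone. A site can comply with both.

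**Step 5: who is affected.** A patient must have CNS metastases or autoimmune disease, a chronic dose above 10 mg/day, added steroids for a treatment-related toxicity, and an event after which resumption is allowed. The documents give no count. The nearest figure is in Section 1.3.4: 69 of 310 patients (69 / 310 = 22%) in the earlier phase II cohort had an adverse event needing systemic steroids. That bears on one of the four conditions only, and Section 1.4 says the earlier studies excluded autoimmune disease, so the rate may not carry over.

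**The case against.** The strongest reply is that the sentence in Section 5.1.2 is not a restart rule. It permits a hold longer than 12 weeks, and restart at the baseline dose is only implied by the point at which the hold ends. The Appendix 11 general rule opens with steroids started for the toxicity, so its limit can be read as applying to those and not to a dose taken since before enrolment. Section 5.1.2 also speaks directly to this population, while Appendix 11 is general guidance, and both leave the length of interruption to documented investigator judgement with the Medical Monitor available.

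Much of this stands. A reader might infer that the texts conflict on any reading, with a 20 mg/day patient restarting at 10, 20 or 20 + 10 = 30 mg/day in total. The documents do not support that: Section 5.1.2 does not require a return to 20 mg/day, so on the added-steroid reading nothing clashes. A reader might also count taper length as a second contradiction. It is not, because Section 5.1.2 is silent on duration and a site that tapers over a month breaches nothing there.

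The mismatch itself remains. Footnote a does the same job as the Section 5.1.2 sentence with a different end point, the added-steroid reading is nowhere stated, and no order of precedence is given. The discretion concerns how long to hold, and re-challenge after long holds or permanent discontinuation; it does not expressly waive the steroid condition for an ordinary restart. The Grade 2 infusion-reaction and cytokine-release row of Appendix 11 has its own re-dosing condition without footnote b, but that is not a chronic-steroid exception.

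**Conclusion.** The point holds as an internal inconsistency that should be corrected. On the total-dose reading, an eligible patient with a baseline above 10 mg/day reaches the Section 5.1.2 end point but cannot satisfy Appendix 11 while staying on that baseline. With CNS metastases the gap is up to 10 mg/day, or a factor of two; with autoimmune disease it has no stated limit. At a baseline of 10 mg/day or less the dose conditions agree.

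This rests on two assumptions: that 10 mg/day is a total dose, and that withholding until a given dose implies resuming at it. The structure of Section 5.1.2 suggests the first, and neither is stated. A reader might go further and conclude that such patients can never restart, or that the subgroup safety results mix two rules. The first is true only while they remain on the baseline dose. The second is a possibility, not a demonstrated effect: the analyses are descriptive, the SAP describes no analysis of restart, and the number affected is unknown and probably small.

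**What to change.** Reconcile Section 5.1.2 with the Treatment Interruption text of Appendix 11 and with footnotes a and b under Tables 1–5, 8–10, 12 and 13:

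1. Put one restart condition for patients on chronic steroids in both places.
2. State whether the mg/day figure is the total dose or only the steroid added for the toxicity.
3. State whether the minimum taper applies to these patients.

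Which condition and which value are for the sponsor's medical team; this review takes no position. The cost is about one sentence in Appendix 11 and a matching edit to the repeated footnotes, with no new data or visits.

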## **NEUROLOGIC DISORDERS**

Myasthenia gravis and Guillain-Barré syndrome have been observed with single-agent atezolizumab. Patients may present with signs and symptoms of sensory and/or motor neuropathy. Diagnostic work-up is essential for an accurate characterization to differentiate between alternative etiologies. Management guidelines for neurologic disorders are provided in [Table 10](#).

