**Table 10 Management Guidelines for Neurologic Disorders**

Event	Management
Immune-mediated neuropathy, Grade 1	

Continue atezolizumab.

Investigate etiology.

Immune-mediated neuropathy, Grade 2	

Withhold atezolizumab for up to 12 weeks after event onset.a

Investigate etiology and refer patient to neurologist.

Initiate treatment as per institutional guidelines.

If event resolves to Grade 1 or better, resume atezolizumab.b

If event does not resolve to Grade 1 or better while withholding atezolizumab, permanently discontinue atezolizumab and contact Medical Monitor.c

Immune-mediated neuropathy, Grade 3 or 4	

Permanently discontinue atezolizumab and contact Medical Monitor.c

Refer patient to neurologist.

Initiate treatment as per institutional guidelines.

Myasthenia gravis and Guillain-Barré syndrome (any grade)	

Permanently discontinue atezolizumab and contact Medical Monitor.c

Refer patient to neurologist.

Initiate treatment as per institutional guidelines.

Consider initiation of 1–2 mg/kg/day oral or IV prednisone or equivalent.

**Appendix 11: Risks Associated with Atezolizumab and Guidelines for Management of Adverse Events Associated with Atezolizumab (cont.)**

---

- a Atezolizumab may be withheld for a longer period of time (i.e., >12 weeks after event onset) to allow for corticosteroids (if initiated) to be reduced to *the equivalent of*  $\leq 10$  mg/day oral prednisone. The acceptable length of the extended period of time must be *based on an assessment of benefit–risk by the investigator and in alignment with the protocol requirements for the duration of treatment and documented by the investigator*. The Medical Monitor is available to advise as needed.
- b If corticosteroids have been initiated, they must be tapered over  $\geq 1$  month to *the equivalent of*  $\leq 10$  mg/day oral prednisone before atezolizumab can be resumed.

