- c Resumption of atezolizumab may be considered in patients who are deriving benefit and have fully recovered from the immune-mediated event. *The decision to re-challenge patients with atezolizumab should be based on investigator's assessment of benefit–risk and documented by the investigator (or an appropriate delegate)*. The Medical Monitor is available to advise as needed.

**Appendix 11: Risks Associated with Atezolizumab and Guidelines for Management of Adverse Events Associated with Atezolizumab (cont.)**

---

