**IMMUNE-MEDIATED MENINGOENCEPHALITIS**

Immune-mediated meningoencephalitis is an identified risk associated with the administration of atezolizumab. Immune-mediated meningoencephalitis should be suspected in any patient presenting with signs or symptoms suggestive of meningitis or encephalitis, including, but not limited to, headache, neck pain, confusion, seizure, motor or sensory dysfunction, and altered or depressed level of consciousness.

Encephalopathy from metabolic or electrolyte imbalances needs to be distinguished from potential meningoencephalitis resulting from infection (bacterial, viral, or fungal) or progression of malignancy, or secondary to a paraneoplastic process.

All patients being considered for meningoencephalitis should be urgently evaluated with a CT scan and/or MRI scan of the brain to evaluate for metastasis, inflammation, or edema. If deemed safe by the treating physician, a lumbar puncture should be performed and a neurologist should be consulted.

Patients with signs and symptoms of meningoencephalitis, in the absence of an identified alternate etiology, should be treated according to the guidelines in [Table 11](#).

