## **IMMUNE-MEDIATED MYOSITIS**

Immune-mediated myositis has been associated with the administration of atezolizumab. Myositis or inflammatory myopathies are a group of disorders sharing the common feature of inflammatory muscle injury; dermatomyositis and polymyositis are among the most common disorders. Initial diagnosis is based on clinical (muscle weakness, muscle pain, skin rash in dermatomyositis), biochemical (serum creatine kinase increase), and imaging (electromyography/MRI) features, and is confirmed with a muscle biopsy.

*Patients with possible myositis should be referred to a rheumatologist or neurologist. Patients with possible myositis should be monitored for signs of myocarditis.*

Patients with signs and symptoms of myositis, in the absence of an identified alternate etiology, should be treated according to the guidelines in [Table 13](#).

**Appendix 11: Risks Associated with Atezolizumab and Guidelines for Management of Adverse Events Associated with Atezolizumab (cont.)**

---

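### For drug-related flares of pre-existing myasthenia gravis or Guillain-Barré syndrome, Section 5.1.2 and Appendix 11 Table 10 give different dosing instructions, opposite at Grade 1, and neither is said to prevail

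*Protocol*

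**What the plan says.** **Who may enter.** Section 4.1.2 (Exclusion Criterion 14) and Appendix 5 allow patients whose autoimmune disease is controlled on 12 weeks of unchanged treatment. The Appendix 5 table lists both Guillain-Barré syndrome and myasthenia gravis.

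**Section 5.1.2, Treatment Interruption.** One sentence refers atezolizumab-related adverse events to Appendix 11 and the Investigator's Brochure. The next covers a new autoimmune disease that those sources do not list, "or for patients with an autoimmune disease who develop a flare, the following dosing guidance should be applied". The guidance is then:
- "Grade 1 event: atezolizumab dosage should be maintained"
- for Grade 2 or 3, "atezolizumab should be suspended until the subject responds to treatment of the autoimmune disease and the disease becomes stable"
- for Grade 4, permanent discontinuation.

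**Appendix 11.** The introduction covers toxicities that are, or may be, due to atezolizumab. In Table 10 the row "Myasthenia gravis and Guillain-Barré syndrome (any grade") calls for permanent discontinuation, contact with the Medical Monitor and referral to a neurologist. Footnote c softens this: "Resumption of atezolizumab may be considered in patients who are deriving benefit and have fully recovered from the immune-mediated event", on a benefit-risk decision that the investigator documents.

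**Precedence.** Section 5.1 names Section 5.1.2, Appendix 11 and the Investigator's Brochure side by side as sources of management guidance. It does not rank them.

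**The concern.** A patient with established myasthenia gravis who has a mild flare on treatment, thought possibly due to atezolizumab, falls under two rules. A site reading Section 5.1.2 gives the next infusion. A site reading Table 10 stops the drug and contacts the Medical Monitor.

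This matters for three reasons. Controlled autoimmune disease is one of the groups that Section 1.4 deliberately brings in, and that section concedes that the effect of checkpoint inhibition on such disease is not well understood. With about 200 sites in about 30 countries (Section 9.5), different readings are likely if such a case arises. And the text treats like cases differently without giving a reason: new-onset Grade 1 myasthenia gravis, being listed in Appendix 11, stops drug, while a Grade 1 flare of existing disease may continue it.

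A lesser effect is on reporting. SAP Section 4.6.2 repeats the adverse event summary, including events leading to drug discontinuation, by history of autoimmune disease. Which rule a site followed could move a patient in or out of that count.

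**Working it through.** No arithmetic from the plan is involved. The check is whether both rules reach the same patient, and what each then says.

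**1. Does the flare rule cover these diseases?** Yes. The restriction to diseases not listed in Appendix 11 attaches to the new-disease limb. The flare limb has no such restriction.

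**2. Does Table 10 cover a flare?** Its neuropathy rows are labelled immune-mediated; the myasthenia gravis and Guillain-Barré row is not, and it does not separate new onset from flare. Other parts of Appendix 11 limit themselves. The meningoencephalitis text applies to "Patients with signs and symptoms of meningoencephalitis, in the absence of an identified alternate etiology" and the myositis text to "Patients with signs and symptoms of myositis, in the absence of an identified alternate etiology"; the myocarditis and renal texts carry the same condition. The neurologic introduction has no such limit. It says only: "Diagnostic work-up is essential for an accurate characterization to differentiate between alternative etiologies".

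**3. When do both apply?** When the flare is judged related or possibly related. That judgement is realistic: Section 5.3.4 (Table 5) treats an event as related unless stated criteria are met, and Section 5.1.1 names both conditions among the risks of atezolizumab. A flare judged unrelated falls under Section 5.1.2 alone.

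**4. Side by side, for a related or possibly related flare:**

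| Grade | Section 5.1.2 | Appendix 11, Table 10 | Result |
|---|---|---|---|
| 1 | Maintain dosing | Permanently discontinue | Opposite immediate action |
| 2 | Suspend; restart once responding and stable | Permanently discontinue; resume only with benefit, full recovery and a documented decision | Drug stops under both; restart differs |
| 3 | As Grade 2 | As Grade 2 | Drug stops under both; restart differs |
| 4 | Permanently discontinue | Permanently discontinue, footnote c still open | Same immediate action |

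Count over the two diseases: opposite action in 1 grade × 2 diseases = 2 combinations; different restart condition in 2 grades × 2 diseases = 4 combinations.

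**5. Is there a tie-breaker?** None in Sections 4.3.2, 5.1, 5.1.1 or 5.1.2, nor in the Appendix 11 introduction. The Investigator's Brochure is not among the documents, so whether it settles the matter cannot be checked.

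**The case against.** The strongest reply is that Section 5.1.2 orders the rules by its structure. A general referral to Appendix 11 is followed at once by a specific rule for a sub-population, so flares would be an exception to the referral. That reading is plausible, but it is not stated. Table 10 is just as specific in the other direction, by disease and for every grade. The ambiguity remains.

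A second reply is that Appendix 11 concerns drug-induced events, and that Section 5.3.4 names a pre-existing medical condition as an alternative cause. This stands as a limit: without attribution to the drug there is no conflict. It does not remove the case where the investigator thinks the drug provoked the flare.

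A third reply concerns Grades 2-3. For a chronic disease, full recovery from a flare may reasonably mean return to the stable baseline, and Section 5.1.2 already asks for a documented benefit-risk assessment before re-challenge after more than 12 weeks. This largely stands. The difference there is one of wording and default, and it is secondary to Grade 1.

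Safeguards also narrow the risk. Exclusion Criterion 14 bars patients with a history of serious or life-threatening immune reactions. Section 4.6.2 requires stopping for any condition that endangers the patient. Table 10's permanent stop can be reversed. None of these corrects an express instruction to keep dosing at Grade 1.

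Finally, timing. SAP version 3.0 is dated December 2022 and describes the data monitoring committee's reviews as past. Few patients, or none, may still be on drug.

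**Conclusion.** The conflict is real but narrow. For flares of pre-existing myasthenia gravis or Guillain-Barré syndrome judged related or possibly related to atezolizumab, the protocol gives opposite instructions at Grade 1 and different restart conditions at Grades 2-3, with no stated precedence. Severity is minor; this is a cheap improvement for patient safety. The number of patients with either disease, or still on treatment, is not in the documents, and the entry limits make it likely to be small.

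The conclusion assumes that the flare is attributed to the drug and that the Investigator's Brochure does not rank the rules.

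A reader might infer a general contradiction between Section 5.1.2 and Appendix 11, extending for example to Grade 3 hepatic and ocular flares. The documents do not support that. In those cases drug stops under both rules, and only the restart wording differs. The hepatic text asks for other causes to be considered, and the ocular text speaks of visual complaints such as uveitis and retinal events. The myocarditis, meningoencephalitis, renal and myositis texts already give way to an identified alternative cause.

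Nor does the point touch the sample size, the precision table or any planned analysis. SAP Section 4.6.2 already counts autoimmune flares of Grade 3 or higher, and both named diseases, as events of special interest.

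**What to change.** Add one sentence to the Treatment Interruption part of Section 5.1.2:

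*Flares of myasthenia gravis or Guillain-Barré syndrome of any grade considered related or possibly related to atezolizumab are managed according to Appendix 11, Table 10, including its re-challenge provision.*

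Flares judged unrelated stay under the existing rule. A blanket clause applying the stricter instruction to every Appendix 11 event should be avoided: it would change the handling of flares not examined here, such as myocarditis, meningoencephalitis, and Grade 2 dermatologic or thyroid flares.

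**Cost.** Section 9.7 requires ethics approval, and regulatory approval where applicable, so the sentence should travel with the next amendment and matters only for patients still on drug. No SAP, database or sample-size change is needed.

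**Downsides.** A few patients with low-grade flares would stop earlier than under Section 5.1.2, softened by documented re-challenge. Dosing for these two diseases would depend on the causality judgement, which the flare rule now ignores. At Grade 4 the sentence carries Table 10's re-challenge option with it; if the sponsor wants none there, the sentence should say so.
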